1 INTRODUCTION AND STUDY DESIGN

1.1 Background

Electronic cigarettes for nicotine delivery

Electronic cigarettes (e-cigarettes) have proliferated at a rapid rate since their introduction into the US market in 2007 and their use as a form of nicotine delivery far outpaced the science base (1, 2). Important questions revolved around their abuse liability and safety. Although the design of these devices continues to evolve, we have previously described nicotine intake, systemic retention, pharmacokinetics, and effects, as well as vaping behavior and self-administration of e-cigarettes (3, 4). We showed that e-cigarettes deliver as much nicotine from 15 puffs as a typical tobacco cigarette (~1 mg), most of which is systemically retained, and the shape of the plasma nicotine concentration-time curve is also similar to tobacco cigarettes, except that the maximum plasma nicotine concentration is, on average, lower for e-cigarettes. During *ad libitum* access, e-cigarettes were vaped intermittently in groups of 2-5 puffs or single puffs such that plasma nicotine levels rose gradually and peaked at the end of the 90-minute session. This differs from the rapid increase in plasma nicotine observed during controlled use of e-cigarettes or during tobacco cigarette smoking. Taken together, these results indicate that e-cigarettes have the potential to produce and sustain nicotine addiction but their use and abuse liability may differ from tobacco cigarette.

Electronic cigarettes are NOT restricted to nicotine

Marijuana is the most widely used illicit drug (5). While marijuana has traditionally been combusted, currently vaping of either loose leaf marijuana or other forms of -9-tetrahydrocannabinol (THC) oil has been increasing (6). The latest national data show that 7.6% of current marijuana users (past 30 days) and 9.9% of ever marijuana users (lifetime) administered THC through a vaporizer or electronic device (6) (the study did not differentiate between vaporizers and electronic devices like e-cigarettes). The prevalence of vaped marijuana or THC is higher among younger adults. Prevalence of vaped marijuana/THC among 18-24 and 25-34 year-old ever marijuana users was 19.3% and 16.3%, respectively, compared to 8.8% for 35-49 year-olds and 5.7% for those 50 years and over (6). A recent study also showed high rates of cannabis vaping using e-cigarettes among high school students (18.0% among ever e-cigarette users) (7).

Combined effects of tobacco and marijuana.

The combined inhalation of tobacco and marijuana is common. Smoking of marijuana in a cigar wrapping (a blunt) is very popular among adolescents and young adults, particularly in the African American population. Smoking of a combination of tobacco and marijuana in cigarette form is also common, particularly in Europe (8) (9). Since both marijuana and tobacco are consumed by vaping, it is likely that vaping of both products will also soon become common. Very little is known about the pharmacology and safety of simultaneous intake of nicotine and THC from vaping.

1.2 RESEARCH QUESTIONS

To understand THC pharmacology and safety of cannabis vaping, including the pharmacology and safety of co-administration of nicotine and THC.

1.3 SPECIFIC AIMS/OBJECTIVES

1. To characterize Δ^9 -tetrahydrocannabinol (THC) delivery, systemic exposure, and effects from vaping THC-containing cannabis leaf alone or cigarette tobacco alone, or the combination of cannabis and tobacco.
2. To assess sympathetic nervous system (SNS) stimulating and subjective SNS-related effects of THC alone compared to nicotine (tobacco) alone or combined to THC and nicotine co-administration.
3. To assess emissions of THC, terpenes, and other compounds from electronic THC delivery devices.

1.4 STUDY DESIGN

1.4.1 Design Summary

The study is designed as a within-subjects single-blinded crossover study. Fourteen smokers of tobacco cigarettes and cannabis will switch between three conditions, namely: (a) vaping cannabis leaf, (b) vaping tobacco containing nicotine and (c) vaping a combination of cannabis leaf and tobacco containing nicotine. All participants will vape each product with the PAX loose-leaf vaporizer.

PAX vaporizers will be purchased by the study team. The cannabis leaf will be obtained through the National Institute on Drug Abuse Drug Supply Program. The tobacco containing nicotine, used in conditions (b) and (c) will come from commercially available Marlboro brand cigarettes. The same amount of cannabis or tobacco will be used in all conditions.

The study will be conducted during three outpatient visits separated by at least 48 hours. The order of treatment (cannabis leaf, tobacco with nicotine, cannabis leaf & tobacco with nicotine) will be counterbalanced between subjects. Subjects will be blinded to the content of the vaporizer on the study day but will be told during screening that they will vape cannabis alone, tobacco alone, and cannabis plus tobacco with nicotine.

1.42 Number of Subjects

A total of 14 subjects will be enrolled in this study over a period of about 6 months. The anticipated accrual rate is approximately 2-4 subjects per month.

1.43 Study Timeline

- Study application was submitted to the Institutional Review Board (IRB): pending
- IRB Approval date: June 14, 2018
- Other approvals:
 - Research Advisory Panel of California: Approved
 - Schedule 1 license from the US DEA: Received
 - Investigational New Drug Application: Approved

1.5 ELIGIBILITY

All individuals interested in participating and who meet the inclusion/exclusion criteria will be invited to be part of the study. Inclusion criteria for participants to be enrolled are described below. Eligibility will be assessed by the Clinical Research Coordinator beginning an eligibility checklist at the time of the online survey. This checklist will be updated during the phone screen and finally after the in-person screening visit.

1.5.1 Inclusion Criteria

- Age ≥ 21 years ≤ 70 years
- Regular user of combustible tobacco cigarettes (at least 1 cigarette weekly)
- Regular user of cannabis in any form administered through the pulmonary route (smoking and/or vaping) at least once a week.
- Positive for THC on screening toxicology test
- Willing to abstain from tobacco smoking and all other combustible products (ex: cigars) for 12 hours prior to each outpatient hospital admission.
- Willing to abstain from smoking/ingesting cannabis for 12 hours prior to each outpatient hospital admission.

- Willing to abstain from using any kind of nicotine products for 12 hours prior to each outpatient hospital admission (ex: electronic cigarettes, nicotine replacement therapy).
- Saliva cotinine ≥ 30 ng/mL and/or NicAlert of 6
- Healthy (based on limited physical examination and medical history collected during screening)
 - Heart rate < 105 BPM
 - Systolic Blood Pressure < 160 and > 90 [*considered out of range if both machine and manual readings are above/below these thresholds*]
 - Diastolic Blood Pressure < 100 and > 50 [*considered out of range if both machine and manual readings are above/below these thresholds*]
 - Body Mass Index ≤ 38.0
 - Women of child-bearing potential must use an acceptable contraceptive during the study

1.5.2 Exclusion Criteria

- Any congenital or acquired immunologic disorders due to the following:
 - Human immunodeficiency virus [HIV] infection
 - Congenital immune deficiency syndromes
 - Chronic diseases (diabetes mellitus, cancer, emphysema, or cardiac failure)
 - Intensive Care Unit care
 - Malnutrition
 - Immunosuppressive therapy of another disease process (e.g., radiation, cytotoxic chemotherapy, anti-graft rejection medication, corticosteroids, monoclonal antibodies directed against a specific component of the immune system)
- Medical (The following unstable medical conditions):
 - Heart disease
 - Seizures or history of seizure disorder
 - Cancer
 - Thyroid disease (okay if controlled with medication)
 - Diabetes
 - Hepatitis B or C or Liver disease
 - Glaucoma
 - Kidney disease or urinary retention
 - History of stroke
 - An ulcer in the past year
 - Active use of an inhaler for Asthma or COPD
 - History of traumatic brain injury with current sequelae
 - History of paranoia after marijuana use

- Psychiatric conditions
 - Current or past schizophrenia, and/or current or past bipolar disorder
 - Major Depression (current or within the past year)
 - Major Personality Disorder
 - Participants with current or past minor or moderate depression and/or anxiety disorders will be reviewed by the study physician and considered for inclusion
 - History of psychiatric hospitalizations are not exclusionary, but study participation will be determined as per study physician's approval
- Drug/Alcohol Dependence
 - Alcohol or illicit drug dependence within the past 12 months with the exception of those who have recently completed an alcohol/drug treatment program and are currently abstaining from drug and alcohol
 - Positive toxicology test for illicit drugs at the screening visit (THC & prescribed medications okay)
 - Opioid Replacement therapy (including methadone, buprenorphine)
 - Scoring a 7 or higher total sum score on the Severity of Dependence Scale for cannabis use.
- Psychiatric medications
 - Current regular use of any psychiatric medications with the exception of SSRIs and SNRIs **and** current evaluation by the study physician that the participant is otherwise healthy, stable, and able to participate.
- Other Medications
 - Use of medications that are inducers of nicotine metabolizing enzyme CYP2A6 (Example: rifampicin, carbamazepine, phenobarbital, and other anticonvulsant drugs).
 - Concurrent use of nicotine-containing medications
 - Any stimulant medications (example: Adderall) generally given for ADHD treatment
 - Use of sympatholytic medications for cardiovascular conditions including hypertension (Example: beta and alpha-blockers)
- Other/Misc. Chronic Health Conditions
 - Oral thrush
 - Fainting (within the last 30 days)
 - Other “life threatening illnesses” as per study physician's discretion
- Use of Other Tobacco Products (OTP); any of the following products in combination more than 15 times in the past month
 - smokeless tobacco
 - pipes
 - cigars

- Pregnancy
 - Pregnancy (self-reported and urine pregnancy test)
 - Breastfeeding (determined by self-report)
- Concurrent participation in another clinical trial
- Inability to communicate in English
- Planning to quit smoking or cannabis use within the next 60 days

1.6 ID AND RANDOMIZATION

1.6.1 Study ID Assignment

Subject IDs will be assigned as follows: XXXX-YYY, where XXXX is the CTSI CRS Study Number and YYY is assigned sequentially once a subject consents to the study during the Screening Visit, starting with XXXX001. Plasma samples and inpatient questionnaire labels will be labeled as follows: XXXX-#-YYY, where # is the study day (1 for day 1, 2 for day 2, 3 for day 3).

1.6.2 Subject assignment to conditions

	1	2	3	4	5	6	7	8	9	10	11	12	13	14
Study Day 1	C	T	C+T	C	T	C+T	C	T	C+T	C	T	C+T	C	T
Study Day 2	T	C+T	C	T	C+T	C	T	C+T	C	T	C+T	C	T	C+T
Study Day 3	C+T	C	T	C+T	C	T	C+T	C	T	C+T	C	T	C+T	C

*Where, C is cannabis leaf; T is tobacco cigarettes; C+T is cannabis leaf + tobacco cigarettes. Order of enrolled subjects will be counterbalanced; order is assigned at admission.

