3.4 PHARMACOKINETIC STUDY: Outpatient Visits

3.4.2 Protocol for Outpatient Study

3.4.1(a) Marijuana preparation

Cannabis leaf material (11.7% THC) obtained from NIDA will be stored frozen in a locked room in the Zuckerberg San Francisco General Hospital Pharmacy. When a participant is randomized, the pharmacy will dispense of 250 mg of cannabis (this includes a back-up supply of 125 mg). All cannabis will then be stored in the freezer compartment of the medication refrigerator in the medication room of the Clinical Research Services Ward 5B.

Cannabis material to be used by a study participant will be humidified 24-36 hours before use. Using a petri dish placed at the bottom of the desiccator, 2 centrifuge tubes, each filled with sodium chloride solution, will be emptied into the dish. Cannabis cigarettes will be placed on the desiccator platform and maintained at room temperature overnight, which is expected to raise the moisture of the cannabis cigarettes by 3 to 5%. Cannabis material will be used within one hour after removal from the humidifier.

3.4.1(b) Hospital Admission Protocol

Before arrival to the hospital, the study co-I or CRC will meet the participant to collect a urine sample for drug testing. Only when it is confirmed that the participant is negative for all drugs other than cannabis, will we admit him/her on the research ward.

Upon arrival at the research ward, the following procedures will occur:

1. Nurses will ask the participant when they last smoked, vaped, or used THC.
 - If the participant smoked cigarettes or vaped e-cigarettes after 10pm the night before either admission, they will be dismissed from the study.
2. An expired CO test will be administered. If their CO reading is greater than or equal to 5 ppm, they will either be dismissed from the study or procedures will be delayed depending on PI discretion.
3. A pregnancy test will be administered to female participants. If the pregnancy test is positive, they will be dismissed from the study.
4. If the participant is female, the pregnancy test will also serve as the voided urine. If the participant is male, they will provide urine sample for discard.

3.4.1 (c) Outpatient Study Protocol

Samples	Time	Activity
STUDY DAY 1 (same procedures as Study Days 2 & 3)		

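### The three rotating treatment orders balance day position but not the preceding condition, so any cannabis carry-over would bias C+T versus C

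*Combined protocol and SAP*

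**What the plan says.** - **Design.** Section 1.4.1 describes a single-blinded crossover of three conditions at visits at least 48 hours apart, whose order "will be counterbalanced between subjects". Section 1.42 adds: "A total of 14 subjects will be enrolled in this study over a period of about 6 months".
- **Assignment.** The table in section 1.6.2 has 14 columns. Its top row reads "Study Day 1 C T C+T C T C+T C T C+T C T C+T C T", and each of the two lower rows moves every entry one step along the same three-condition cycle. The footnote says "Order of enrolled subjects will be counterbalanced; order is assigned at admission".
- **Randomization.** The word stands in the heading of section 1.6, and section 3.4.1(a) says "When a participant is randomized, the pharmacy will dispense of 250 mg of cannabis". No random method is described anywhere.
- **Analysis.** Section 6.3 plans a mixed model ANOVA with sex as covariate, and the comparison it names is THC only against THC plus nicotine. It names no period, sequence or carry-over term. Baseline adjustment is stated for nicotine only.
- **Baselines.** Section 3.4.3 lists a THC tube at B1, drawn before the session on every study day.

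**The concern.** A three-period crossover of three conditions has six possible orders. Using only the three cyclic ones balances the day on which each condition falls, but ties each condition to a single predecessor. The contrast that section 6.3 names, cannabis alone against cannabis with tobacco, then compares C sessions that mostly come straight after a study cannabis session with C+T sessions that never do. Residual THC, or tolerance left by that session, would enter the estimated effect of adding tobacco. The planned model has nothing to separate the two.

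The study being described as not hypothesis-driven does not remove the problem. Shifted averages and confidence intervals mislead in a descriptive study too, and between-condition tests are still planned.

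**Working it through.** **1. Counts from the table in section 1.6.2.**

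| Order | Columns | n |
|---|---|---|
| C → T → C+T | 1, 4, 7, 10, 13 | 5 |
| T → C+T → C | 2, 5, 8, 11, 14 | 5 |
| C+T → C → T | 3, 6, 9, 12 | 4 |

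The total is 5 + 5 + 4 = 14, which matches section 1.42. The documents give no power calculation, so there is no other design figure to reproduce.

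Position: day 1 has C 5, T 5, C+T 4; day 2 has T 5, C+T 5, C 4; day 3 has C+T 5, C 5, T 4.

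Predecessors: T before C+T, 5 + 5 = 10; C before T, 5 + 4 = 9; C+T before C, 5 + 4 = 9. The three reverse pairs never occur.

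**2. Bias without a period term.** Every subject has each condition once, so the estimate of C+T minus C is the difference of two means over 14 sessions. Let c(X) be the shift that condition X leaves on the next visit.

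Bias = (10/14) c(T) - (9/14) c(C+T) = +0.714 c(T) - 0.643 c(C+T).

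Assume equal residue L after C and C+T and none after T. Then 0 of 14 C+T sessions and 9 of 14 C sessions follow cannabis, so the bias is 0/14 - 9/14 = **-0.643 L**.

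**3. Bias with subject and period fitted (least squares).** Bias = +0.692 c(T) - 0.667 c(C+T) - 0.026 c(C). Under the same assumption it is **-0.692 L**, so a period term alone does not help.

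**4. How far this depends on the assumption.**
- All three conditions leave the same shift: 0.714 - 0.643 = +0.071 L without period, and zero with period.
- The effect persists across an intervening tobacco visit: 5 of 14 C+T sessions (those in C → T → C+T) and 9 of 14 C sessions have earlier study cannabis. The bias is 5/14 - 9/14 = -0.29 L without period.
- No carry-over: zero.

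**5. Cost of modelling carry-over.** With 14 subject, 2 period, 2 treatment and 2 carry-over parameters the design has full rank (20 of 20), so the terms can be estimated. The variance of C+T minus C rises from 0.144 to 0.744 sigma², where sigma² is the within-subject variance. The ratio is 0.744/0.144 = 5.2, so the standard error is 2.3 times as large.

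**6. All six orders at n = 14.** Use each order twice (12 subjects); every ordered pair then occurs 4 times. Add C → T → C+T and its mirror C+T → T → C. Neither places one cannabis condition straight after the other, so the bias is 4/14 - 4/14 = 0. It is also 0 with period fitted. The worst choice of two extra orders, for example C → C+T → T and T → C → C+T, gives 6/14 - 4/14 = 0.14 L. Across choices the contrast variance is 0.143 to 0.145 sigma² without carry-over terms and 0.17 to 0.19 sigma² with them.

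**The case against.** The documents do not show that L differs from zero. Visits are at least 48 hours apart. Participants are at-least-weekly cannabis users who need abstain for only 12 hours before a visit, so their own use may outweigh a three-puff study session. Baselines are taken on each day. Section 6.3 treats heart rate and blood pressure as changes, so a simple additive residue would cancel there, and nicotine PK is baseline-adjusted. All of this stands as reason to expect a modest L for some outcomes. It does not cover THC and 11-OH-THC, for which no baseline adjustment is stated, nor tolerance, which a change score does not remove.

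Four stronger readings are tempting, and the documents do not support them:
- **That carry-over does bias the contrast.** The bias is conditional on an L that nobody has given.
- **That carry-over is aliased with treatment.** The full-rank result shows heavy confounding, not aliasing.
- **That the plan is wrong to call the order counterbalanced.** The word is accurate for day position and fails only for predecessors. The 5/5/4 split is minor.
- **That a predictable order lets staff select who gets what.** The columns are not labelled as enrolment order, and everyone is assigned all three conditions, so there is little room for selection.

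The database guide in Appendix A describes catecholamine data from numbered participants. Sessions therefore appear to have been run, and a new list may come too late for them.

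**Conclusion.** The point holds as a conditional weakness that costs little to remove. The assignment is systematic, uses three of six orders, and fixes the predecessor of every condition on days 2 and 3. If a study cannabis session leaves a shift L on the next visit, equal after C and C+T and absent after T, then C+T minus C is off by -0.64 L, or -0.69 L with period fitted. Under other carry-over patterns the size changes, as shown in the working. The planned analysis neither adjusts for nor examines this in THC outcomes, and adding carry-over terms to this layout makes the contrast variance about five times as large.

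The arithmetic is certain given the table. The size of L is not, so this is no finding that the results are biased.

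**What to change.** **If assignments can still be changed**
- Replace the table with a random list over all six orders, each used two or three times among 14. Let the two orders used three times be C → T → C+T and C+T → T → C. Describe how the list is generated.
- Add period to the mixed model in section 6.3.
- Adjust THC and 11-OH-THC outcomes for the pre-session B1 value, as is planned for nicotine.

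**For sessions already run**
- Describe the assignment as systematic, not randomized.
- Add period and the pre-session THC adjustment.
- Report a carry-over sensitivity analysis, and say that period alone does not remove the bias and that the carry-over model will be imprecise.

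**Separately**, reconcile two passages on timing. Section 1.6.2 assigns the order at admission, while section 3.4.1(a) says "Cannabis material to be used by a study participant will be humidified 24-36 hours before use". The two can conflict on day 1 unless cannabis is prepared for everyone, which is not stated. This is a scheduling matter and has no bearing on the carry-over argument.

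**Cost.** A new list and a few lines of analysis text. No extra participants, visits or blood draws, and no meaningful loss of precision: 0.143 to 0.145 sigma² against 0.144 sigma² now.

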1.7 PARTICIPANT WITHDRAWAL

1.7.1 Dropouts and compensation

If a participant declares they are no longer interested in completing the study, they will be considered a “dropout.” If the participant decides to stop participating in the study prior to outpatient admission for study day 1, they will only receive compensation for the Screening Visit (i.e. \$30).

- Complete study day 1: \$100
- Complete study day 2: \$100
- Complete study day 3: \$100
- For complying with all study procedures including attending the orientation visit, abstaining from tobacco cigarettes, nicotine products, and marijuana use 12

hours prior to Study Days 1, 2 and 3, subjects will be given an additional \$120 bonus (\$40 each day).

- Total possible compensation is \$450.

1.7.2 Lost to Follow Up

If a participant is unable to be contacted and does not respond to calls from the Clinical Research Coordinator (up to three unsuccessful phone contact attempts), he/she will be considered “lost to follow-up” (LTFU). Before a participant is considered LTFU, every effort will be made to contact him/her. After being considered LTFU no further outreach will be conducted. If a formerly LTFU participant re-contacts the CRC outside a given study window, participant will be rescheduled for screening.

2 STUDY TIMELINE

2.1 VISIT SCHEDULE & WINDOWS OF ASSESSMENTS

Assessment Point	Maximum Time from REDCap Questionnaire Screen
REDCap Questionnaire	
In-Person Screening Visit	14 days from REDCap questionnaire
Orientation	45 days* (~1 month from in-person screening)
Study Day 1	47 days
Study Day 2	49 days
Study Day 3	51 days

*In-person screening may be repeated if this window is exceeded.

3 STUDY VISITS AND PROCEDURES

3.1 REDCap Questionnaire

Interested participants will fill out a short (10-minute) survey on REDCap. The CRC will complete an eligibility checklist, beginning at the time of this online survey. This checklist will be labeled first by the REDCap ID and later by the Study ID after consent & assignment. The Clinical Research Coordinator (CRC) will then determine if the participant is eligible to attend a Screening Visit based on above inclusion/exclusion criteria.

